#### **4.4 Supportive Care**

Primary pain management for the participant is of consummate importance. Investigators expect for participants to receive standard pain management, which could include IV fluids, opioid pain medicine, NSAIDS, and/or other interventions. Participants may show additional clinical signs warranting evaluation, such as fever or hypoxia, and will be evaluated appropriately.

Orders for standard pain management or other clinical interventions may be performed concurrently with administration of study drug. Caregivers are encouraged to refer to hospital policy for assessing, documenting, and reporting pain and other symptoms to the clinical team. Comprehensive sickle cell care will be managed by the Hematology team.

### **5.0 DRUG/DEVICE/BIOLOGIC AGENT INFORMATION**

To allow for the study team and participants to remain blinded to the treatment assignment, the study drug will be labeled by the pharmacy as Gabapentin/Placebo (PMVOC 100 mg/mL) followed by applicable dose and administration instructions.

#### **5.1 GABAPENTIN (Neurontin®)**

**Source and Pharmacology:** Gabapentin is a white to off-white crystalline solid that is freely soluble in water. Its mechanism of action in preventing

seizures is not known. Gabapentin is not appreciably metabolized in humans; pharmacological effects are from the activity of the parent compound. It is eliminated unchanged in the urine. Patients with renal impairment should have dosage adjustments. Administration with food has little effect on absorption of gabapentin. In a single-dose gabapentin pharmacokinetics study in healthy infants and children, the mean maximum concentration was achieved 2.31 hours after a single oral dose in 48 children ages 1 month to 12 years of age. Dosing for 1 month to 2 years of age of the immediate-release gabapentin syrup was 10 mg/kg. Dosing for children greater than 2 years of age of the immediate-release capsules was based on weight and ranged from 8 mg/kg to 12.5 mg/kg as follows: 200 mg for 16 to 25 kg; 300 mg for 26 to 36 kg; 400 mg for 37 to 50 kg. The mean maximum concentrations were 3.74 mcg/mL for < 5 years of age (n=27) and 4.52 mcg/mL for ≥ 5 years of age (n=21). The single dose of gabapentin was well tolerated with seven participants reporting mild treatment-associated adverse events. The adverse events included asthenia, truncal ataxia, dizziness, drowsiness, somnolence, and vomiting [79].

**Formulation and Stability:** Gabapentin is supplied as an oral suspension containing 100 mg/mL. The St. Jude Children's Research Hospital Pharmacy will compound an oral suspension from commercially available capsules following pediatric drug formulation worksheets previously agreed upon by the FDA (Appendix IV). The oral suspension is stable for 3 months under refrigerated conditions between 2 and 8°C (36 and 46°F). The oral suspension will be stored between 2 and 8°C (36 and 46°F) in amber plastic prescription bottles for up to 3 months with continuous temperature monitoring.

**Toxicity:** Patients 3 – 12 years old treated with gabapentin for epilepsy reported the following central nervous system related adverse events: emotional lability, hostility, thought disorder and hyperkinesia in addition to CNS depression (dizziness, somnolence, fatigue, ataxia, and nystagmus). In placebo controlled trials of gabapentin in children taking other antiepileptic drugs, the following were also seen at higher frequency in the treatment group than the placebo group: viral infection, bronchitis, pharyngitis, rhinitis, respiratory infection, coughing, otitis media, fever, nausea and/or vomiting, diarrhea, depression, headache, diplopia, blurred vision, nervousness, seizures, pruritus, dyspepsia, constipation, weight gain, anorexia, leukopenia, back pain, and peripheral edema.

Do not administer within two hours of aluminum or magnesium containing antacids.

**Supplier:** Commercially available

**Dosage and Route of Administration:** Participants randomized to the active treatment arm will receive approximately 15 mg/kg gabapentin PO one time, as soon as feasible after enrollment. The maximum dose is 900mg (9mL).

## 5.2 PLACEBO

Patients randomized to the placebo arm will receive oral suspension similar in appearance, quantity and taste to the active treatment arm. Placebo suspension will be compounded with commercially available suspending and flavored syrup vehicles (Ora Plus/Ora Sweet) with flavoring added (Appendix V). The solution will be stored in the refrigerator. Placebo suspension will be prepared by the St. Jude Children's Research Hospital Pharmacy.

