#### **3.2 Exclusion Criteria**

- 3.2.1 Prior randomization in this study.
- 3.2.2 Mild pain (score  $< 4$ ), or pain for which treatment with opioid is not indicated.
- 3.2.2 Pregnant or lactating females.
- 3.2.3 Decreased GFR ( $< 60 \text{ml/min}/1.73\text{m}^2$ ) as estimated by the revised Schwartz equation.
- 3.2.4 Current treatment with gabapentinoid drugs (gabapentin or pregabalin).
- 3.2.5 Known seizure disorder.
- 3.2.6 Current treatment with antiepileptic agents.

- 3.2.5 Pain in combination with other clinical symptoms that require additional interventions, including fever with focus, acute chest syndrome, acute injury, or splenic sequestration.
- 3.2.6 Allergy to gabapentin.
- 3.2.7 Current participation in another research study with an IND/IDE agent (including SCATE and TWiTCH trials).
- 3.2.8 Inability or unwillingness of research participant or legal guardian/representative to give written informed consent.

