## **4.0 TREATMENT PLAN**

### **4.1 Treatment**

Upon each participant’s enrollment, study staff will randomize the participant to one of 2 possible treatment arms (see section 11 for randomization procedure) and order the study treatment. The pharmacy will dispense the dose of study treatment ( gabapentin vs. placebo) to the clinic or medicine room as soon as possible.

Study drug and other interventions will be administered and documented according to hospital policy by any appropriate clinical staff. All caregivers and study personnel will be blinded to the treatment assignment. Based on previous research experience at St. Jude, administration of the study drug is estimated to occur no later than 2 hours after patient’s first opioid pain medication in the acute care setting.

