## **6.2 Evaluations During Therapy**

Data for research purposes will be collected from the hospital medical records for the event, including visit duration, pain scores, and IV administered pain interventions given, as performed according to hospital standards of care. Only St. Jude pharmacists are unblinded to treatment assignment.

Pain assessments throughout the acute event will be performed by any clinical staff as per hospital standards (Appendix II). Researchers will analyze pain scores at baseline (at presentation), 15 minutes prior to or 15 minutes after the time of study drug administration, at 3 hours after study drug administration, and at point of decision for either admission or discharge to home (for patients who continue to be treated for pain longer than 3 hours after study drug is administered).

The pain scales used are the numerical rating system, the Faces Pain Scale, and the FLACC pain scale (for patients 7 years or older, ages 4-6 years, or less than 4 years, respectively) (Appendix II). Patients unwilling or unable to provide a score on the age-appropriate scale may use another scale if indicated.

Clinicians will obtain other studies as needed for good patient care.

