**Gabapentin (for PMVOC)** \_\_\_\_\_ **oral solution** \_\_\_\_\_ **100mg/mL** \_\_\_\_\_ **120mL**  
(Generic Name) \_\_\_\_\_ (Dosage Form) \_\_\_\_\_ (Concentration) \_\_\_\_\_ (Final Quantity)

**Stability:** 91 days

**Stability Reference:** Pedia Neuro, 1999

*Label:*

**Store:** Refrigerated 2-8 C

Ingredient	Amt. Required	Amt. Used	Manufacturer / Lot #
Gabapentin capsule	300mg	40	
Ora-Plus and Ora-Sweet	50mL of each		
Anise Oil	3gtt/5mL	3.6mL	
Peppermint Oil	2gtt/5mL	2.4mL	

*Directions:*

Measure and add the 50mL of each Ora-Plus and Ora-Sweet to a prescription bottle. Empty the contents of all of the Gabapentin capsules into the bottle. Cover and shake the contents until the drug is evenly dispersed. Then add the appropriate measurements of the Anise oil and Peppermint oil. Cover again and shake to mix all ingredients well. Transfer the drug to a graduated cylinder to determine the remaining volume needed to qs to 120mL. Return to prescription bottle. Rinse the cylinder with the predetermined 1:1 Ora-Plus and Ora-Sweet. Add to bottle and shake. Label the bottle appropriately.

For Investigational Use Only

PLACE LABEL HERE

Created: 03/24/00

Updated:

Prepared By: \_\_\_\_\_

Checked By: \_\_\_\_\_

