## Pediatric Drug Formulation

Gabapentin Placebo (for PMVOC (Generic Name)	Oral Solution (Dosage Form)	60 mL (Concentration)	60 mL (Final Quantity)
---	--------------------------------	--------------------------	---------------------------

Stability: 14 days

Stability Reference: USP 795, pg 34

Label:

Store: Refrigerate 2-8 C

Ingredient	Amt. Required	Amt. Used	Manufacturer / Lot #
Microcrystalline Cellulose placebo caps size 0	1cap/10mL	6 caps	
Ora-Plus and Ora-Sweet		29.1 mL of each	
Anise Oil	1gtt/5mL	0.6 mL	
Peppermint Oil	2gtt/5mL	1.2 mL	

Directions:

Measure and add the Ora-Plus and Ora-Sweet to a prescription bottle. Empty the contents of each placebo capsule into the bottle. Cover and shake well until the ingredients are well dispersed. Add the Anise and Peppermint oils and shake well to mix all ingredients.

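### The active and placebo recipes specify anise oil at 3.0% and 1.0% with no stated reason and no matching check, so the taste similarity claimed in section 5.2 is unsupported and the blind is at some risk.

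*Combined protocol and SAP*

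**What the plan says.** Section 5.2 describes the placebo this way: "Patients randomized to the placebo arm will receive oral suspension similar in appearance, quantity and taste to the active treatment arm". It says the placebo is made from Ora Plus and Ora Sweet "with flavoring added (Appendix V"). Section 5.1 says pharmacy compounds the active suspension by the Appendix IV worksheet, which it describes as previously agreed with the FDA. Section 5.2 makes no such statement about Appendix V.

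The worksheets give these flavouring entries:

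| | Appendix IV (active) | Appendix V (placebo) |
|---|---|---|
| Final quantity | 120 mL | 60 mL |
| Anise oil | 3 drops per 5 mL; 3.6 mL | 1 drop per 5 mL; 0.6 mL |
| Peppermint oil | 2 drops per 5 mL; 2.4 mL | 2 drops per 5 mL; 1.2 mL |

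On blinding, section 4.1 says: "All caregivers and study personnel will be blinded to the treatment assignment". Section 6.2 adds that only the pharmacists know the assignment. Section 5.0 gives both products the same label name. Section 8.2 lists unblinding of the participant or the study team as a reason for coming off study. On who rates pain, section 6.2 says: "Pain assessments throughout the acute event will be performed by any clinical staff as per hospital standards".

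**The concern.** Two liquids made to these recipes differ threefold in a strongly aromatic ingredient, while section 5.2 says they are similar in taste. The protocol does not explain the difference, describes no comparison of the finished products, and plans no check of whether blinding succeeded.

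The outcomes are open to expectation. The primary outcome is a pain score, self-reported at most ages and rated by an observer with FLACC below 4 years. Opioid use (secondary) and admission (exploratory) depend on decisions by treating staff. A participant receives one dose and cannot compare products, since section 3.2 excludes "Prior randomization in this study". Staff are different. At one hospital, the same person could give several of the 166 doses over about four years and also score pain or manage opioids. If staff noticed two recurring scents and linked one to gabapentin, ratings and decisions could shift, and no analysis could remove the effect afterwards.

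**Working it through.** **1. Are the worksheet figures internally consistent?** Drops in the batch = (drops per 5 mL) × volume / 5. Dividing by the stated millilitres gives the implied drops per mL.

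- Active anise: 3 × 120 / 5 = 72 drops; 72 / 3.6 = 20 per mL.
- Placebo anise: 1 × 60 / 5 = 12 drops; 12 / 0.6 = 20 per mL.
- Active peppermint: 2 × 120 / 5 = 48 drops; 48 / 2.4 = 20 per mL.
- Placebo peppermint: 2 × 60 / 5 = 24 drops; 24 / 1.2 = 20 per mL.

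All four entries fit one drop factor. The placebo calls for "29.1 mL of each" of the two vehicles, and 2 × 29.1 + 0.6 + 1.2 = 60.0 mL, so the lower anise amount is built into the recipe. For the active, the directions say to "determine the remaining volume needed to qs to 120mL", and 40 × 300 mg / 120 mL = 100 mg/mL, the stated strength. A misread table or a batch-size effect is therefore unlikely: peppermint scales with batch size and anise does not.

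**2. Concentrations** (oil volume / final volume).

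- Anise, active: 3.6 / 120 = 3.0%.
- Anise, placebo: 0.6 / 60 = 1.0%. The ratio is 3.
- Peppermint: 2.4 / 120 = 2.0% and 1.2 / 60 = 2.0%.
- Total flavouring oil: 5.0% against 3.0%.

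**3. At the largest administered volume.** Section 5.1 says "The maximum dose is 900mg (9mL"). A 9 mL dose contains 9 × 0.03 = 0.27 mL of anise oil (5.4 drops) in the active arm and 9 × 0.01 = 0.09 mL (1.8 drops) in the placebo arm.

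**4. What a bias would do, if there were one.** This illustration says nothing about whether anise causes bias. Inputs from section 11.1 are a 45% placebo response, looks at 96 and 166 participants (48 and 83 per arm), and one-sided nominal thresholds of 0.0143 and 0.0447. The test is a pooled Z-test and the drug is taken to have no true effect. The assumed quantity is the shift in apparent response in the gabapentin arm. Each range is with and without applying the futility stop.

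| Assumed shift | Chance of a false positive |
|---|---|
| −5 points (staff guess the wrong way) | about 1% |
| None | about 5–6% |
| +1 point | about 6.5–7% |
| +2 points | about 8–9% |
| +5 points | about 16–17% |
| +10 points | about 35–38% |

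**5. Arithmetic for a common rate.** At 3 drops per 5 mL, 60 mL of placebo needs 36 drops, and 36 / 20 = 1.8 mL of anise oil (1.8 / 60 = 3.0%). To keep 60 mL, each vehicle becomes (60 − 1.8 − 1.2) / 2 = 28.5 mL.

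**The case against.** The strongest reply is that composition is not perception. Section 5.2 promises similarity, not identity, and does not mention smell. The active contains 100 mg/mL of drug and the placebo none, so equal oils need not taste equal, and extra anise might be how similar taste is reached. This stands as a possibility. The documents neither state nor exclude it, and masking the drug's taste would not by itself remove a difference in scent.

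The route to unblinding is also limited. Both products carry one label name, and staff who noticed two scents would still need another clue to know which was gabapentin. Enrolment of about 42 a year is less than one dose a week. Doses and pain scores may come from any clinical staff, so few individuals would compare many doses. Most scores from age 4 upward are the patient's own. These points lower the risk without removing it. Somnolence, the expected side effect, is a separate possible route that matching the flavour leaves untouched.

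A reader might also infer a visible difference from the capsule counts: 40 per 120 mL (3.3 per 10 mL) in the active against 1 per 10 mL in the placebo. The documents do not support that. The counts refer to different materials, no fill weight is given for the cellulose capsules, and section 5.1 describes gabapentin as freely soluble in water.

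**Conclusion.** The mismatch is real and exact: anise oil at 3.0% in the active and 1.0% in the placebo, with peppermint equal at 2.0%. It is unexplained, and no check of the finished products is described, so the recipes do not support the statement in section 5.2 that the two are similar in taste.

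The consequence is a risk to the blind, mainly through staff exposed to repeated doses. A reader might conclude that the products are perceptibly different or that the blind has failed. Neither follows, because there are no sensory data and a deliberate reason is possible. Nor can the false-positive figures be read as the expected effect of the anise difference. They rest on assumed shifts that nothing in the documents ties to flavouring, and the direction could be the opposite. The size of any bias is unknown.

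The stated dose strength, the endpoint, the sample size and the analysis are unaffected. The point deserves correction because lost blinding cannot be repaired in analysis and the remedy is small.

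**What to change.** Reconcile Appendices IV and V with section 5.2.

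- If the difference is not deliberate, revise only the placebo worksheet to the active's anise rate: 3 drops per 5 mL, which is 1.8 mL per 60 mL, with each vehicle reduced from 29.1 to 28.5 mL. The active worksheet agreed with the FDA and its stability support then stay as they are.
- If the extra anise is there to mask the taste of the drug, say so in section 5.2.
- In either case, have pharmacy compare coded samples of the two products for smell, taste and appearance, and adjust the placebo only until they cannot be told apart. Record the result.

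The cost is one worksheet revision or a sentence of explanation, plus a brief pharmacy check. It needs no extra participants or visits and no change to the sample size or analysis.

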## 6.0 REQUIRED EVALUATIONS, TESTS, AND OBSERVATIONS

Subsections of 6.0 are in tabular form in Appendix I.

### 6.1 Pre-Study Evaluations

At a minimum, one baseline pain assessment will be documented in the medical record upon presentation to the acute care setting. Participants may have received opioids or other pain relieving interventions from home supply prior to arrival.

Prior to enrollment, glomerular filtration rate estimate will be calculated using the Schwartz equation based on the patient's most recent clinically obtained creatinine value documented in MILLI not more than 6 months prior to the pain event.

Female patients of childbearing potential must have documentation in MILLI of negative pregnancy test not more than 2 weeks prior to enrollment. Females currently receiving Depo-Provera at St. Jude may use documentation of negative pregnancy up to 6 weeks prior to enrollment. Female participants without negative test on record as described should have negative test documented in MILLI prior to enrollment. Either serum or urine testing may be used.

## **6.2 Evaluations During Therapy**

Data for research purposes will be collected from the hospital medical records for the event, including visit duration, pain scores, and IV administered pain interventions given, as performed according to hospital standards of care. Only St. Jude pharmacists are unblinded to treatment assignment.

Pain assessments throughout the acute event will be performed by any clinical staff as per hospital standards (Appendix II). Researchers will analyze pain scores at baseline (at presentation), 15 minutes prior to or 15 minutes after the time of study drug administration, at 3 hours after study drug administration, and at point of decision for either admission or discharge to home (for patients who continue to be treated for pain longer than 3 hours after study drug is administered).

The pain scales used are the numerical rating system, the Faces Pain Scale, and the FLACC pain scale (for patients 7 years or older, ages 4-6 years, or less than 4 years, respectively) (Appendix II). Patients unwilling or unable to provide a score on the age-appropriate scale may use another scale if indicated.

Clinicians will obtain other studies as needed for good patient care.

## **6.3 Response Evaluations**

No special tests and/or evaluations are required to evaluate response during study treatment. Significant pain will be treated by the primary care team as clinically indicated.

## **6.4 Off-Study Evaluations**

Pain scores will be captured at 3 hours after the study drug is administered. The 3 hours post study drug pain score may be obtained up to 30 minutes before or after the 3 hour time point. The 3 hours post study drug pain score can be collected either in person or via phone. Patients who need additional pain management or other care will have a pain score at the time of decision for admission or discharge home.

Participants will be taken off study after a toxicity evaluation is performed / attempted within 72 hours following study drug administration (see section 7.2).

## 6.5 Long-Term Follow-up Evaluations

No long-term evaluations are planned.

Participants will be notified of their treatment assignment (gabapentin or placebo) after the completion of data collection for the last participant enrolled. Notification will be performed by a member of the study team in person (when feasible) or by letter at the earliest convenience of the study team and documented in the study files.

## 7.0 EVALUATION CRITERIA

### 7.1 Response Criteria

The response to therapy will be measured by pain intensity scores and total opioid use as described in the study objectives.

### 7.2 Toxicity Evaluation Criteria

Toxicity will graded according to the NCI CTCAE (version 4.0). Only new or worsening problems (i.e. significant changes in lab values from baseline) occurring after the administration of study drug will be captured for this study, as sickle cell patients may have steady-state or pre-existing values that fall in the range of toxicity per the CTCAE (e.g. anemia, fever, pain). Worsening pain scores after enrollment will not be captured or reported as AEs, but will be managed clinically. Hospital admission for VOC is an expected outcome and will not be captured/reported as an AE.

All participants must remain at St. Jude for at least 3 hours following administration of study drug to allow for monitoring of toxicity.

Participants that were discharged will be contacted by study staff between 24 and 72 hours following the administration of study drug to screen for unexpected events. Patients that were admitted after administration of the study drug will be monitored through hospital records to determine if any unexpected events occurred. These patients will also be contacted directly by study staff. Patients will remain on study until discharged so all clinical notes can be reviewed to determine toxicity.

## 8.0 CRITERIA FOR REMOVAL FROM PROTOCOL THERAPY AND OFF-STUDY CRITERIA

## **8.1 Off-therapy criteria**

Because study therapy consists of a single oral dose of study drug, there are no off-therapy criteria. Refer to section 8.2, Off-Study Criteria.

## **8.2 Off-Study Criteria**

- 8.1.1 Death
- 8.1.2 Lost to follow-up
- 8.1.3 Request of the Patient/Parent
- 8.1.4 Refusal of therapy
- 8.1.5 Discretion of the Study PI, such as the following
  - The researcher decides that continuing in the study would be harmful
  - A treatment is needed that is not allowed on this study
  - The participant's condition gets worse
  - New information is learned that a better treatment is available, or that the study is not in the participant's best interest
- 8.1.6 Study evaluations are complete
- 8.1.7 Unblinding of participant or study team to participant's treatment assignment

## **9.0 SAFETY AND ADVERSE EVENT REPORTING REQUIREMENTS**

### **9.1 Reporting Adverse Experiences and Deaths**

Principal investigators are responsible for promptly reporting to the IRB any adverse events that are unanticipated, serious, and that may represent potential harm or increased risk to research participants. When an unanticipated death occurs, the PI should report it to the Director of the Office of Human Subjects' Protection immediately, by phone: [REDACTED]

A reportable event entry into TRACKS should follow within 48 hours. Serious, unanticipated, and related or possibly related events must be reported within 10 working days. At the same time, the investigator will notify the study sponsor (NIH or pharmaceutical company), cooperative group, and/or the FDA, as appropriate. To report adverse events in gene therapy trials,

investigators should use specific RAC forms found at [http://www4.od.nih.gov/oba/RAC/Adverse\\_Event\\_Template.doc](http://www4.od.nih.gov/oba/RAC/Adverse_Event_Template.doc).

The principal investigator is responsible for reviewing the aggregate toxicity reports and reporting to the IRB if the frequency or severity of serious toxicities exceed those expected as defined in the protocol or based on clinical experience or the published literature. Any proposed changes in the consent form or research procedures resulting from the report are to be prepared by the study team and submitted with the report to the IRB for approval.

The following definitions apply:

A serious event refers to any event in which the outcome is fatal or life-threatening, results in permanent disability, causes inpatient hospitalization or prolongs existing inpatient hospitalization, or is a congenital anomaly, cancer, or overdose. Hospitalization due to the presenting VOC will not be reported as a serious event.

An unanticipated adverse event refers to those not identified in their nature, severity, or frequency in the current risk documents (e.g., investigator's brochure), or consistent with the investigational plan.

The following are considered reportable: Any injuries, serious event or other unanticipated adverse events involving risk to participants or others which occur at a frequency above that considered acceptable by the investigators and the IRB. (FDA) As described in HRPP Policy 01.720, the OHSP Director or designee performs the initial review of unanticipated problems or serious adverse event reports. Internal reports of events that are unanticipated, serious, and related or possibly related to study interventions or procedures are then forwarded to the IRB Chair or designee and if necessary, referred to the full IRB. Based on the frequency and seriousness of adverse events, the IRB Chair or Committee may deem it necessary to suspend or terminate a research study or studies.

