## **9.2 Reporting to the Sponsor and/or Federal Agencies**

### **9.2.1 Notification of Federal Agencies by Investigator**

Copies of all correspondence to the St. Jude IRB, including serious adverse event reports, are provided to the St. Jude Office of Regulatory

Affairs via the electronic reporting system (TRACKS). All FDA related correspondence and reporting will be conducted through the Regulatory Affairs Office.

The FDA will be notified in writing (IND safety report) of any serious and unexpected adverse event associated with an investigational treatment or device. Annual reports, which will include the up-to-date clinical and safety data, will be submitted to the FDA at least annually.

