#### **9.2.2 Recording Adverse Events and Serious Adverse Events**

Adverse events will be evaluated and documented by the clinical staff and investigators. The CRAs are responsible for documenting adverse events and entering them into the CRIS protocol-specific database. AEs that are classified as serious, unexpected, and at least possibly related will be reported expeditiously to the St. Jude IRB as described in protocol section 9.1. All other events will be reported to the IRB as part of the continuing review process.

As stated in section 7.2, only new or worsening problems occurring after the administration of study drug will be reported as adverse events, as sickle cell patients may have pre-existing conditions that fall in the range of toxicity per the CTCAE and are not related to study drug (e.g. anemia, fever, pain). Any event occurring more than 72 hours after administration of study drug will not be captured.

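### The closed list of serious events in section 9.1 omits important events that needed intervention to prevent a listed outcome, so some unexpected toxicity treated in clinic would miss expedited reporting

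*Combined protocol and SAP*

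**What the plan says.** Section 9.1 sets out seriousness in one sentence. It begins "A serious event refers to any event in which the outcome is fatal or life-threatening, results in permanent disability, causes inpatient hospitalization" and ends "or prolongs existing inpatient hospitalization, or is a congenital anomaly, cancer, or overdose". The next sentence makes an exemption: "Hospitalization due to the presenting VOC will not be reported as a serious event". Section 7.2 likewise keeps VOC admission out of adverse event capture.

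Three rules depend on that definition:

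- **IRB, section 9.1:** "Serious, unanticipated, and related or possibly related events must be reported within 10 working days".
- **IRB, section 9.2.2:** expedited reporting for events that are serious, unexpected and at least possibly related. For the rest, "All other events will be reported to the IRB as part of the continuing review process".
- **FDA, section 9.2.1:** "The FDA will be notified in writing (IND safety report) of any serious and unexpected adverse event associated with an investigational treatment".

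Section 10.2 requires continuing review at least once a year.

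On toxicity, section 5.1 lists behavioural effects "in addition to CNS depression (dizziness, somnolence, fatigue, ataxia, and nystagmus". The Protocol Summary names somnolence as the expected side effect. Section 7.2 says "All participants must remain at St. Jude for at least 3 hours following administration of study drug to allow for monitoring of toxicity".

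**The concern.** Definitions of this kind usually have a last criterion for an event that met none of the named outcomes only because someone intervened. Section 9.1 has none, and this trial's design makes such events plausible. A drug with listed CNS depression is given alongside opioids (4.4, 11.2) to participants from age 1 (3.1.3). Section 5.1 gives a mean time to peak concentration of 2.31 hours after a single oral dose in children, inside the 3-hour stay required by 7.2. Acute toxicity is therefore likely to appear where staff can treat it before a listed outcome occurs.

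Two pieces of wording add to the gap. The phrase about the outcome being life-threatening can be read as the end result, which would leave out a dangerous event that was reversed. The VOC exemption gives no rule for a child admitted with both VOC pain and a drug-related event.

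At stake is how soon the IRB and FDA hear of an unexpected harm from adding gabapentin to opioids, and whether the trial's serious-event count reflects it.

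**Working it through.** The plan states no figure on this point, so the check applies the definition to cases.

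**Conditions for prompt reporting**

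- Expedited IRB report = serious AND unanticipated or unexpected AND at least possibly related (9.1, 9.2.2).
- FDA safety report = serious AND unexpected, for an event associated with the treatment (9.2.1).
- Anything else goes to continuing review for the IRB (9.2.2) and to the annual report for the FDA (9.2.1).

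**Step 1: is the event serious under 9.1?**

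| Case | As written | With the fix |
|---|---|---|
| A. Respiratory depression, life-threatening when it occurs, reversed in clinic | Serious if judged at the time; not serious if only the end result counts | Serious |
| B. Sedation or respiratory depression that itself causes or prolongs admission | Serious, but no rule if the child is also admitted for VOC | Serious |
| C. Event due to an overdose | Serious | Serious |
| D. Event needing intervention in clinic to prevent a listed outcome, judged not life-threatening, no event-related admission, no overdose | Not serious | Serious |
| E. Ordinary somnolence | Not serious | Not serious |

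The gap is case D, together with the end-result reading of case A and mixed admissions in case B.

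**Step 2: is the event unexpected?** Section 9.1 calls an event unanticipated if its nature, severity or frequency is not identified in the risk documents. Somnolence is named as expected, so sedation fails this second condition unless its severity or frequency is unanticipated. Respiratory depression is not in the toxicity list of section 5.1. On the protocol text, seriousness is then the condition that decides whether it is expedited.

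**Step 3: is there another prompt route?**

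- Section 9.1 also makes injuries and other unanticipated adverse events involving risk reportable. This does not strictly require seriousness, but it carries a qualifier about frequency above an acceptable level and gives no clock of its own.
- Section 9.3 sends an emergency unblinding to the IRB on the SAE timeline even without an SAE. It applies only if someone unblinds.
- The investigator's aggregate review in 9.1 concerns serious toxicities, so it depends on the same definition.
- The interim analysis in 11.1 covers efficacy and futility only.

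None of these reliably brings forward a first case D event.

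**Step 4: how long could the wait be?** Section 11.1 expects 63 patients evaluated a year, with two thirds enrolled: 63 × 2/3 = 42 a year, or 42/2 = 21 per arm. If the event falls just after a review, reviews are exactly a year apart and no Step 3 route is used, about 42 further participants could be enrolled first. This is an upper bound, not an expected value.

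**The case against.** The strongest reply is that the definition is wider than it first looks. It includes life-threatening events, events that cause or prolong admission, and overdose. Respiratory depression that needs urgent reversal can reasonably be called life-threatening even when treatment works. A reader might infer that 9.1 counts only final outcomes, or that toxicity treated in time can never be serious. The text does not support either inference, and this part of the reply stands in full. It leaves case D untouched.

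The VOC exemption is also narrow. It covers admission due to the presenting VOC, and nothing tells investigators to attribute a sedation admission to VOC. That stands too; what is missing is a rule for mixed admissions.

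Third, a reader might infer that the IRB could learn of such events only at annual review. The reportable-event paragraph of 9.1 and section 9.3 show that is too absolute. Nor are the events lost: new or worsening toxicity is graded by CTCAE (7.2) and entered in the database (9.2.2). What is delayed is prompt notice.

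Fourth, unexpectedness is a separate condition, so a new seriousness criterion would not bring forward reports of ordinary sedation. This is correct and limits the benefit.

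Finally, the Monitoring Plan (10.2) and HRPP Policy 01.720 (9.1) may deal with such events. They were not available. The rules in 9.2.1 and 9.2.2 still rest on the term as 9.1 defines it.

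**Conclusion.** The concern holds in a limited form. Section 9.1 has no criterion for an important event that needed intervention to prevent a listed outcome, and its life-threatening wording is ambiguous. Followed as written, an unexpected, possibly related event that is treated in clinic, judged not life-threatening and causes no event-related admission is not serious. It goes to continuing review, with only partial cover elsewhere.

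The documents give no rate for such events, and none can be derived from them. A reader might be tempted to apply an assumed toxicity rate to the 83 participants per arm. That would give the chance that an event occurs, not the chance that it is classed as non-serious, so it does not measure this gap. The only figure the plan supports is the worst-case wait of about 42 enrolments, under the conditions in Step 4.

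The conclusion assumes that respiratory depression would count as unexpected. That follows from section 5.1, but other risk documents could change it. It also assumes that neither the Monitoring Plan nor the HRPP policy fills the gap. The point concerns safety oversight and does not affect the efficacy analysis. An amendment is worthwhile.

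**What to change.** Make three changes to section 9.1:

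1. Add to the list: *or is an important medical event that required intervention to prevent one of these outcomes*.
2. State that life-threatening is judged at the time of the event, not by how it ended.
3. State that the exemption for VOC admission does not remove an event that separately qualifies as serious.

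Sections 9.2.1 and 9.2.2 can stay as they are. The gain is for events of unlisted nature, or of unanticipated severity or frequency. Before amending, the sponsor should check the Monitoring Plan and HRPP Policy 01.720, so that all the documents use one definition.

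The cost is a few sentences and possibly a few more expedited reports, with no change to treatment, sample size or analysis.
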